## 1 BACKGROUND

Cystinuria is an inherited autosomal recessive disorder of the kidney that is the result of a defect in the dibasic amino acid transporter in the apical membrane of the renal proximal tubule and small intestine. The disease causes hyperexcretion of cystine, lysine, arginine, and ornithine into the urine. Of these amino acids, only cystine is poorly soluble in urine. Supersaturation of cystine in the urine produces crystals that precipitate and form calculi, which can be a cause of obstruction, infection, and chronic kidney disease. Cystine stone disease has an estimated prevalence of up to 1 in 1,000 in some parts of Europe and 1 in 17,000 in the United States, and comprises up to 2% of all kidney stone disease overall and up to 10% of stone disease in children. As it is a rare disease, pharmaceutical treatments for cystinuria are considered “orphan drugs” based on the U.S. Orphan Drug Act of 1983, which was passed to encourage pharmaceutical companies to develop treatments for diseases with a small market. However, cystine stones constitute a major health challenge for affected individuals because of the frequent recurrence of painful symptoms and the current absence of effective, patient-accepting treatment.

Two primary factors known to affect the solubility of cystine include are cystine concentration and pH. Therefore, the current mainstays of therapy include aggressive hydration to 2.5 to 3 liters of fluid intake daily, lowering of dietary sodium intake, urinary alkalization to pH >7.0, and thiol derivative medications to bind urinary cystine to reduce urinary cystine concentrations to less than 250 mg/l, the level above which cystine becomes insoluble in urine. Thiol derivatives in current use including D-penicillamine and alpha-mercaptopyrionylglycine increase the solubility of cystine by forming more soluble mixed amino acid-disulfide products. However, these medications are difficult to tolerate due to their side effect profiles and, therefore, compliance is poor. Furthermore, the medications require regular monitoring of complete blood count, liver enzymes, and urinary protein excretion. In our own kidney stone clinic population, even when compliance is high, cystinuric patients taking D-penicillamine and alpha-mercaptopyrionylglycine often continue to form recurrent cystine stones. It is not surprising that because cystinuria is a lifelong disease and current medical management is difficult to achieve and not very effective, these individuals have frequent stone recurrences and a higher risk of kidney loss compared to the average calcium oxalate stone former. Therefore, additional well-tolerated and effective medical therapies to treat cystinuria are desperately needed.

## 2 STUDY RATIONALE

One potential therapeutic is the thiol-containing compound alpha-lipoic acid (thioctic acid, 5-(1,2-dithiolan-3-yl) pentanoic acid, ALA). ALA is an over-the-counter supplement and antioxidant found in nutrition supplement stores. ALA is a naturally occurring compound involved with mitochondrial energy metabolism as an enzymatic cofactor. ALA is both synthesized in the body as well as absorbed in the diet. Once ALA is transported into the cell, it is reduced to dihydrolipoic acid (DHLA). Both ALA and DHLA have direct antioxidant activity, and they can regenerate endogenous

antioxidants including ascorbic acid and vitamin E. ALA can also increase intracellular coenzyme Q10^12 and glutathione levels. ALA and DHLA also have additional biochemical effects as metal chelators, reactive oxygen species scavengers, and modulators of signaling transduction of several pathways.

While the potential therapeutic effects of ALA have been studied in a number of diseases including, including Alzheimer's disease, obesity, cardiovascular disease, hypertension, and several cancers, the efficacy of ALA has been best studied in type 2 diabetic peripheral neuropathy. Safety of long-term administration of once- daily 600mg ALA over 4 years was established in the NATHAN 1 trial. Doses up to 1200 mg daily have also been used and appear well tolerated. Given this history safe use in clinical medicine and, most importantly, based upon our positive findings of ALA effectiveness in a mouse model of cystinuria (described below), we propose a pilot study on the use of this supplement in cystinuric participants.

At present we can only hypothesize on the possible mechanism(s) of action of ALA. First, ALA may modulate intracellular cysteine levels through its effects on the cystine/glutamate exchanger and thereby increase glutathione production. Second, ALA may counteract oxidative stress by induction of nuclear factor erythroid related factor 2 (Nrf2), which is involved in cellular cystine uptake. Third, ALA may directly reduce insoluble cystine to form a mixed-disulfide compound to increase urinary solubility of cystine. Fourth, ALA may reduce zinc levels in the kidney, which has been identified as a cofactor in stone formation. No matter which mechanism(s) ultimately emerge(s) as the appropriate explanation, we believe that oral administration of lipoic acid will decrease the amount of quantitative urinary cystine and, most critically, slow the rate of stone formation and growth, thereby reducing the frequency of stone events in cystine stone formers.

In our lab, a mouse model of cystinuria lacking the *Slc3a1* gene was employed to study the formation and growth of urinary cystine stones. *Slc3a1*-/- male mice develop cystine stones at about 2-3 months of age and accumulate stone volume at an approximate rate of 1 mm^3/day, measured by micro-computed tomography. In initial work, 1-month old *Slc3a1*-/- mice were treated with ALA administered through supplementation in the diet (0.5% by weight). By day 45, 1 of 8 mice on the ALA-supplemented diet had developed stones, in contrast to 7 of 7 control mice fed a regular chow diet. In addition, 3-month old untreated stone-forming mice that were then fed ALA grew cystine stones at a dramatically slower rate (stone volume accumulation 10% of controls, n=9) over 120 days. In summary, these initial results show that ALA markedly slows the initiation of cystine stone formation as well as the growth of existing stones. Moreover, based upon body weight, feeding behavior and activity level ALA appears to be very well tolerated in the mouse.

To date, there have been no published studies on the effect of ALA in human stone formers.

## 2.1 Risk / Benefit Assessment

ALA is an over-the-counter supplement and naturally occurring antioxidant. Safety and tolerability of ALA has been demonstrated in several large randomized, placebo-controlled

trials for the treatment of diabetic polyneuropathy. In the SYDNEY 2 trial, diabetic participants received once-daily oral ALA at 600mg, 1,200 mg, or 1,800 ALA over 5 weeks. Rates of adverse events compared to placebo were higher with higher dosing but primarily isolated to minor gastrointestinal side effects. Other large, placebo-controlled randomized trials reported no severe adverse events at 1,200 mg daily dosing. In the longest prospective trial (NATHAN 1) currently published, 600mg ALA daily was administered in 230 diabetic participants in the treatment arm over 4 years. Rates of noncompliance (<10%) and discontinuation due to treatment tolerability (<1%) were similar in both groups. No statistically significant differences were seen in serious adverse events between the two groups. Furthermore, dose-adjustment is not necessary in individuals with chronic renal insufficiency, which is relevant in a population of chronic kidney stone formers, as it does not affect the pharmacokinetics of ALA. Therefore, we do not anticipate a significant number of adverse side effects from administration based on prior studies at the same dose

### 3 STUDY OBJECTIVES

#### 3.1 Primary Objective

The primary objective of this study is to determine the effect of ALA on kidney stone recurrence in participants with cystinuria. Stone recurrence in this study will be assessed in two ways:

- 1) symptomatic stone recurrences, defined as renal colic, stone passage, or surgical removal of a stone.
- 2) silent stone recurrences classified as stone growth or new stones, diagnosed on the basis of renal ultrasound, plain KUB x-ray, or, if clinically indicated, computed tomography.

#### 3.2 Secondary Objectives

The secondary objectives of this study are to determine the effect of ALA on quantitative urinary cystine, cystine solubility, and metallomic and metabolomics profiles in participants with cystinuria. Quantitative urinary cystine is determined by 24-hour urine collection. The metallomic and metabolomics profiles of urine and stone samples will be compared in our lab as a new set of markers to understand how ALA has an effect on the stone-forming process and how its efficacy can be followed during treatment.

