## PROTOCOL SYNOPSIS

TITLE	The effect of lipoic acid natural supplement on cystine stone formation
SPONSOR	[name]
FUNDING ORGANIZATION	FDA
NUMBER OF SITES	1 site
RATIONALE	
Cystinuria is an inherited autosomal recessive disorder of the kidney that is the result of an inability to reabsorb cystine from the urine. Supersaturation of cystine in the urine produces crystals that precipitate and form stones in the kidney, which can be a cause of obstruction, infection, and chronic kidney disease. Cystine stones constitute a major health challenge for affected individuals with cystinuria because of the frequent recurrence of painful symptoms and the current absence of effective, patient-accepting treatment.
 
The naturally occurring oral supplement alpha lipoic acid (ALA) has been shown in a mouse model of cystinuria to dramatically slow the initiation of cystine stone formation as well as the growth of existing stones. To date, there have been no published studies on the effect of ALA in individuals with cystinuria.

STUDY DESIGN	This study will be a single center, randomized double-blind placebo-controlled trial designed to assess how daily 1200 mg ALA supplementation for three years affects kidney stone recurrence, quantitative urinary cystine, and stone, blood and urinary metabolomic and metallomic profiles.
PRIMARY OBJECTIVE	Determine the effect of ALA on kidney stone recurrence in participants with cystinuria.
SECONDARY OBJECTIVES	Determine the effect of ALA on quantitative urinary cystine, and metallomic and metabolomics profiles in participants with cystinuria.
NUMBER OF PARTICIPANTS	50
PARTICIPANT SELECTION CRITERIA	
Inclusion criteria: males and females age 18 or older; documented cystinuria on prior 24-hour urine collection and/or stone analysis; history of previous cystine kidney stones; and being able and willing to provide consent.
 
Exclusion criteria: poorly controlled diabetes mellitus (hemoglobin A1C > 8.0% for more than 1 year); current ALA administration at the time of screening; ALA administration within the last year prior to screening; vulnerable populations including incarceration status; anticipation of

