	pregnancy during the study duration; unable to give informed consent; non-English primary language; pregnancy, lactation, or child- bearing age without birth control devices; and serious illness likely to cause death within the next 5 years.
TEST PRODUCT, DOSE, AND ROUTE OF ADMINISTRATION	The test product is 600 mg of ALA administered orally twice a day for three years.
CONTROL PRODUCT, DOSE AND ROUTE OF ADMINISTRATION	The control product is a sucrose tablet containing 10 mg of sucrose, given orally twice a day for three years.
DURATION OF PARTICIPATION AND DURATION OF STUDY	Screening: 1 week to determine eligibility Treatment: 3 years with visits every 4 months Follow-up: 2 years with visits every 4 months

CONCOMITANT MEDICATIONS	
Allowed: The participants will be allowed to continue any medications they are currently taking.
 
Prohibited: No medications will be strictly prohibited. However, alpha-mercaptobutyrylthiolglycine and D-penicillamine, two medications currently used to treat cystinuria, are both thought to bind the sulfhydryl groups of cysteine preventing the molecules from binding together and resulting in the insoluble cystine molecule. Both medications are not used with great frequency and both are not very effective. As they may interfere with the mechanism of action of ALA, participants of this study who take alpha-mercaptobutyrylthiolglycine and/or D-penicillamine will be asked to stop these medications 12 weeks prior to starting the treatment portion of the study as a washout period to ensure no harmful effects result from stopping these therapies. If they chose not to stop, at the discretion of the Principal Investigator, the participant will be allowed to participate and the study will simply document the use of Thiola throughout the course of the study and may look at these participants separately in the final analysis.

EFFICACY EVALUATIONS	Efficacy evaluations will include determination of stone recurrences on clinical history, exam, and radiographic review; quantitative 24-hour urinary cystine; and urinary, blood, and stone metallomic and metabolomic profiling.

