PRIMARY ENDPOINT	
The primary efficacy endpoint will be assessed in two ways over the course of the 3-year treatment period:
 
 
1) symptomatic stone recurrences, defined as renal colic, stone passage, or surgical removal of a stone;
 
2) silent stone recurrences, classified as stone growth or new stones,
 

	diagnosed on the basis of renal ultrasound, plain KUB x-ray, or if clinically indicated, computed tomography.
SAFETY EVALUATIONS	After participants are enrolled at 3-4 weeks during the treatment period, a study coordinator will contact each participant to check compliance, tolerability, and side effects with ALA supplementation. Any concern for a potential adverse event will be reviewed by the study investigators. Patient clinical care will continue as per the current standard for the duration of this study. Tolerability and side effects will be reviewed at each scheduled clinic visit which normally occur every four months. All reported adverse events will be reviewed by the study investigators. Depending on the severity of the adverse event, the study investigator may determine the need for un-blinding, and the participant may be advised to stop ALA intake if it is determined that ALA is the cause.
PLANNED INTERIM ANALYSES	When 50% of target participants have been enrolled and on the study protocol for 6 months, an interim analysis will be performed by an un-blinded statistician to evaluate for ALA clinical effects.
STATISTICS Primary Analysis Plan	The analysis will be performed on the intention-to-treat principle in the treatment and placebo groups. The primary efficacy endpoint will be assessed by comparing the rates of symptomatic and silent stone recurrences using the t-test with a two-sided p-values and calculated 95% confidence intervals. In addition, the analysis of secondary endpoints will compare quantitative urinary cystine, and metallomic and metabolomics profiles using repeated measures of analysis of variance.

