Clinical data including medical history, plain KUB x-ray and renal ultrasound, routine blood work, and 24-hour urine collections for all participants will be collected as part of normal clinical care at routine clinical visit intervals, which currently occur every 4 months. Routine clinical care for participants will not be altered in any way outside of administration of the supplement or placebo. Routine clinical care generally consists of office visits every 4 months at which time, as medically necessary as determined by the study investigator, an imaging study is performed (plain KUB x-ray, ultrasound, or CT scan if clinically indicated), a 24-hour urine collection is done to check quantitative urinary cystine levels, and blood is drawn to evaluate electrolyte levels as well as renal function. During routine visits for blood and urine tests, any discarded blood and urine specimens will be collected for research testing. No additional blood draw or urine collection will be performed for this study. From discarded routine specimens provided during these clinic visits, metallomic and metabolomics profiling will be performed for all participants using discarded samples material. This is comprised of mass spectrometry and elemental analysis of samples performed in our research lab. Quality of life measurement, as recorded by the Wisconsin Stone-quality of life questionnaire (Wisconsin Stone-QoL), will also be evaluated.

Recurrent stone events, defined by symptomatic or silent stone recurrence, is the primary endpoint in this study. It will be documented in this study cohort, and compared between treatment and placebo groups to determine treatment effect. If stones are removed for surgery or spontaneously passed by participants, any discarded stone specimens not needed for clinical care will also be subjected to metabolomic and metallomic analysis.

At the end of the three years of study drug treatment, all participants will undergo a low dose non-contrast CT scan to look for a silent change in stone size. As this is a pilot study, recruitment will be limited to target enrollment of 50 participants (25 for each treatment arm). Treatment will continue for a total of 3 years and after treatment completion, participants will be followed for an additional 2 years to evaluate for change in clinical status or adverse events resultant from ALA administration.

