### **15.1 Data Sets Analyzed**

Data sets from all participants enrolled in the study will be analyzed.

The primary efficacy endpoint will be assessed by medical history and physical exam, in addition to radiographic imaging performed at each study visit.

The secondary efficacy endpoints will be assessed by 24-hour urine collections (Litholink, Chicago, IL), and the analysis of the metallomic and metabolomics profiles of urine and stone samples that are collected.

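### Stone profiles count as an efficacy measure, but only participants who pass a stone or have one removed supply a specimen, so the comparison of arms is not a randomised one

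*Combined protocol and SAP*

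**What the plan says.** The synopsis (Study Design) includes among the things the trial will assess under ALA the "stone, blood and urinary metabolomic and metallomic profiles". Its Efficacy Evaluations row lists "urinary, blood, and stone metallomic and metabolomic profiling". Section 15.1 assesses the secondary efficacy endpoints by 24-hour urine and by "the analysis of the metallomic and metabolomics profiles of urine and stone samples that are collected". Section 3.2 sets the aim as the effect of ALA and adds: "The metallomic and metabolomics profiles of urine and stone samples will be compared in our lab as a new set of markers", both to explain how ALA acts and to monitor its efficacy.

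On method, the Statistics row of the synopsis says "The analysis will be performed on the intention-to-treat principle in the treatment and placebo groups" and that the secondary analysis will "compare quantitative urinary cystine, and metallomic and metabolomics profiles using repeated measures of analysis of variance". No separate rule is given for stones.

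On supply, section 4.1 reads "If stones are removed for surgery or spontaneously passed by participants, any discarded stone specimens not needed for clinical care" and sends that material for profiling. Sections 10.1 to 10.5 and Appendix 1 list stone collection at every visit, but only when a participant brings one. Sections 3.1, 5.1 and 15.2 define passage and surgical removal as symptomatic recurrences, which are part of the primary endpoint.

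**The concern.** Whether a participant has a stone specimen is decided after randomisation, by events that ALA is meant to prevent. If ALA halves those events, fewer ALA participants contribute, and those who do lean towards people with a strong tendency to form stones. The arms can then differ in average stone profile because different people are represented, even if ALA leaves composition untouched. A real effect could equally be blurred. Participants without a specimen cannot be analysed by intention to treat, and the plan does not say how they are handled.

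At stake is the use of stone composition as evidence of mechanism and as a marker of efficacy. That reading needs a randomised contrast, and these specimens do not supply one.

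**Working it through.** The plan gives no figure for expected specimens or contributors, so there is none to reproduce. The sample sizes in section 15.3 concern event rates; only those rates are used here.

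**Inputs from the documents.** Placebo rate 1 event per person-year and ALA rate 0.5 (section 15.3); 3 years of treatment and 25 per arm (section 4.1).

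**Assumptions.** The documents do not give the share *s* of events that yields a specimen, or the variance *v* of stone-forming propensity between participants (gamma, mean 1, with Poisson events given propensity). Dropout is ignored.

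**Step 1: contributors.** Let m = 3 × rate × s. The expected number per arm with at least one specimen is 25 × [1 − (1 + v·m)^(−1/v)]. With v = 0.5 this is 25 × [1 − (1 + 0.5m)^(−2)].

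| Setting | m | Expected contributors |
|---|---|---|
| s = 1, placebo | 3 | 25 × (1 − 2.5^−2) = 25 × 0.840 = 21.0 |
| s = 1, ALA | 1.5 | 25 × (1 − 1.75^−2) = 25 × 0.673 = 16.8 |
| s = 0.5, placebo | 1.5 | 16.8 |
| s = 0.5, ALA | 0.75 | 25 × (1 − 1.375^−2) = 25 × 0.471 = 11.8 |

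Other assumptions at s = 0.5 give 19.4 versus 13.2 (v = 0, plain Poisson), 15.0 versus 10.7 (v = 1) and 12.5 versus 9.2 (v = 2). For s from 0.25 to 1 and v of 0, 1 or 2, the contributing share differs between arms by about 12 to 25 percentage points.

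**Step 2: how the contributors differ.** With v = 0.5, mean propensity among contributors is [1 − (1 + 0.5m)^(−3)] / [1 − (1 + 0.5m)^(−2)].

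- m = 3: 0.936 / 0.840 = 1.114
- m = 1.5: 0.8134 / 0.6735 = 1.208
- m = 0.75: 0.6153 / 0.4711 = 1.306

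The ALA-minus-placebo gap is 1.208 − 1.114 = 0.094 at s = 1 and 1.306 − 1.208 = 0.098 at s = 0.5. The SD of propensity is √0.5 = 0.707, so the gap is 0.13 to 0.14 SD.

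**Step 3: from propensity to a marker.** Take a marker that ALA does not affect but that is linearly related to propensity with correlation ρ. Its spurious gap is ρ times the Step 2 gap: 0.3 × 0.13 = 0.04 SD up to 0.7 × 0.14 = 0.10 SD. A simulation with v = 1 and 2, s = 0.25, 0.5 and 1, and ρ from 0.3 to 0.7 also gave about 0.04 to 0.10 SD. The correlations are assumptions.

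**Step 4: what could be detected.** With 15.0 versus 10.7 contributors (s = 0.5, v = 1), the difference detectable with 80% power at two-sided 5% is (1.96 + 0.84) × √(1/15.0 + 1/10.7) = 2.80 × 0.400 = 1.12 SD. The spurious gap is about a tenth of that or less.

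**Step 5: fit of the method.** Repeated-measures ANOVA expects a series of measurements per participant at set visits. Here the outcome decides whether a specimen exists and how many there are; some participants give none and others several. The plan does not say whether stones handed in at Visit 1 (before treatment) or at Visits 11 to 16 (after it) enter the comparison. Entry requires previous stones and section 10.1 lists no baseline imaging, so a stone passed on treatment may predate ALA.

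**Step 6: the other specimens.** Sections 9.2.1 and 10 to 10.5 make blood draws conditional on medical need, yet the synopsis counts blood profiling as an efficacy evaluation. For urine, sections 10.1 to 10.5 and Appendix 1 list 24-hour testing at each visit without condition. Section 9.2.3 makes it depend on medical need, section 4.1 can be read the same way, and research urine is leftover material that may not be available.

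**The case against.** **The text does not clearly assign this test to stones.** The section 3.2 sentence does not mention arms, and the ANOVA sentence does not name stones. That is fair as a reading of each sentence. But the synopsis sets out to assess how ALA affects stone profiles, section 15.1 uses them for secondary efficacy endpoints, and no other method is offered. At the least, the plan has no valid method for stones.

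**Stronger readings.** A reader might infer that the comparison is selected on the whole primary outcome. It is not: colic without passage, and silent growth or new stones on imaging, need yield no specimen. A reader might also infer that nearly all placebo participants supply a stone. That requires every event to yield one and no variation between people (25 × (1 − e^−3) = 23.8), whereas the imbalance in Step 2 arises only if people do vary. A reader might further infer that an observed difference would be mostly artefact. Steps 3 and 4 do not support that, and if ALA does not change passage or removal, this mechanism produces no bias between arms.

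**It is minor.** The endpoint is secondary and mechanistic, the trial calls itself a pilot, and section 15 promises a detailed SAP. This limits the weight of the point. It does not remove it, because nothing in the present text restricts the stone comparison.

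**Urine is conditional too.** This stands, and it changes the remedy: moving the comparison to urine does not by itself secure samples from every randomised participant.

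**Conclusion.** The point holds in a limited form. Stone profiles carry efficacy status, but they come only from participants with a passage or removal event, so the contrast between arms is not randomised and the named method does not fit it. If ALA works as assumed, about 21 versus 17 participants contribute at full specimen yield, or about 17 versus 12 at half yield. These counts rest on the plan's event rates, a frailty variance of 0.5 and no dropout.

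The likely bias is modest: about 0.04 to 0.10 SD in an unaffected marker if its correlation with propensity is 0.3 to 0.7, figures the documents do not supply. The case rests on the lost randomised comparison and the small numbers, not on a large distortion. Blood profiles share the problem of clinically driven sampling, but no size has been put on it. The change should be made; it does not affect the primary analysis.

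**What to change.** In the synopsis, section 3.2 and section 15.1:

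- Base the between-arm analysis of metallomic and metabolomic profiles on urine from scheduled visits, in participants with available samples, using a method that tolerates missing visits.
- Reconcile sections 4.1 and 9.2.3 (urine according to medical need) with sections 10.1 to 10.5 and Appendix 1 (24-hour urine at every visit). Until that is done, the urine analysis cannot be described as covering all randomised participants.
- Label stone profiles, and blood profiles from clinically indicated draws, as exploratory and conditional on having a specimen, with no efficacy claim.
- Report the number of participants and specimens per arm, and separate on-treatment stones from Visit 1 and post-treatment stones.

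The labelling and reporting changes are wording only, and no specimen is lost. Reconciling the urine sections requires a decision by the sponsor. The price is that a formal efficacy claim from stone composition is given up.
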